## **11.7 Study Audits**

The sponsor or an external party may undertake a routine audit of the study site dependent on risk assessment pre-study and/or ongoing study conduct. During the course of the study and after its completion, it is likely that one or more quality assurance audits will be undertaken by authorised sponsor representatives or external parties. The purpose of the audit, which is independent of and separate from routine monitoring, will be to evaluate trial conduct and compliance with the protocol, SOPs, GCP and the applicable regulatory requirements.

## **11.8 Quality Assurance Reviews**

### **11.8.1 Eligibility Reviews**

#### **11.8.1.1 Informed Consent and Other Eligibility Reviews**

As per GC requirements, reviews of consent forms will be performed to determine that Informed Consent was obtained before registration on the trial. Throughout the trial, copies of relevant documents (such as clinical history notes, pathology/histology reports, etc.) may be requested for source data verification.

## 12 ADVERSE EVENT REPORTING

### 12.1 Definitions

**Adverse Event (AE):** An AE is any untoward medical occurrence (toxicity, sign or symptoms) in a patient administered a study treatment; the event does not necessarily have a causal relationship with the treatment.

**Serious Adverse Event (SAE):** An SAE is any untoward medical occurrence that occurs after administration of the Ixekizumab .

- Results in death
- Is life-threatening (an event in which the participant was immediately at risk of death *at the time of event*)
- Requires in-patient hospitalisation or prolongation of existing hospitalisation
- Results in persistent or significant disability/incapacity
- Is a congenital anomaly/birth defect
- Important medical event (events may be considered a serious adverse experience if they require medical or surgical intervention to prevent one of the listed definitions, e.g. an 'allergic bronchospasm' which required intensive treatment in an emergency room or at home)

An event will not be considered to be a SAE if;

- Hospitalisation is due to pre-trial scheduled elective surgery
- Out-patient hospitalisation for procedures such as:
  - Elective day surgery
  - Convenience purposes (e.g. transportation difficulties)

**Serious Adverse Reaction (SAR):** A serious adverse reaction is an SAE that is suspected as having a causal relationship to the trial treatment, as assessed by the investigator responsible for the care of the patient. A suspected causal relationship is defined as possibly, probably or definitely related (see definitions of causality table).

**Related Unexpected Serious Adverse Event:** An adverse event that meets the definition of serious and is assessed by the Principal Investigator or nominative representative delegated and trained by the Principle Investigator as:

Related	that is, it resulted from administration of any of the research procedures
Unexpected	that is, the type of event is not listed in the protocol as an expected occurrence

### Definitions of causality:

Relationship	Description
Unrelated	There is no evidence of any causal relationship with the trial treatment
Unlikely	There is little evidence to suggest there is a causal relationship (e.g. the event did not occur within a reasonable time after administration of the trial treatment). There is another reasonable explanation for the event (e.g. the patient's clinical condition, other concomitant treatment)
Possible	There is some evidence to suggest a causal relationship (e.g. because the event occurs within a reasonable time after administration of the trial treatment). However, the influence of other factors may have contributed to the event (e.g. the patient's clinical condition, other concomitant treatments)
Probable	There is evidence to suggest a causal relationship, and the influence of other factors is unlikely
Definitely	There is clear evidence to suggest a causal relationship, and other possible contributing factors can be ruled out

## 12.2 REPORTING

### 12.2.1 Adverse Events (AE)

Adverse events are to be reported following any injection of Ixekizumab, which must be graded according to The National Cancer Institute (NCI) Common Terminology Criteria for Adverse Events (CTCAE) version 5.0 (Appendix) by a study investigator. For each AE, the highest grade observed since the last visit should be reported on the relevant CRF.

All adverse events shall be recorded in the trial database via adverse event CRFs. Internal statistical analysis of these data shall be performed at the times specified in the protocol and investigators and responsible HRECs will be advised of any safety issues which emerge during this process.

Of note, all serious adverse events are to be reported within 24 hours to Lilly Ltd who provides the drug for this study.

### **12.2.2 Serious Adverse Events (SAE)**

SAEs are to be reported by the trial site immediately and no more than 24 hours of being notified, from the commencement of injection until the last visit. Date of the SAE occurrence and date notified must be documented.

The investigator at the trial site is responsible for;

- grading the event according to the NCI CTCAE v 5.0
- identifying the seriousness of the adverse event
- identifying the causal relationship to the treatment and
- determining the expectedness according to the treatment

The investigator is also responsible for notifying responsible HRECs, Research Governance Officers or other appropriate regulatory authorities of the SAE according to local ethical and regulatory guidelines. They are also to follow up the event (with regular reporting) until resolved. Please see figure 1.

[figure not shown]
The Sponsor shall;

- Arrange for the trial chairperson and/ or a clinical reviewer to review the event and confirm causal relationship and expectedness
- Report applicable events to the regulatory authorities (e.g Therapeutic Goods Administration of Australia (TGA))

Notify all other participating investigators of any serious unanticipated related adverse events and any action taken

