### 2.3.2 Secondary Endpoints

- Drug related adverse events and serious adverse events at 12 weeks.
- Percentage reduction in ulcer size at 12 weeks compared to the initial wound size.
- Percentage patients with healed ulcers
- Time to ulcer healing
- Percentage and absolute reduction in Pain score (0-10)
- Changes in Quality of life DLQI score
- Compliance with compression
- Treatment-related reduction of IL17 levels in wound fluid and biopsies\*
- Wound-infiltrating macrophage phenotype change from M1 to M2\*
- Alterations in wound microbiome

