## 7 TRIAL PARTICIPANT ASSESSMENTS

### 7.1 Trial Participant Assessment Table

Assessment	Compression Bandage Treatment				Pre Screening	Drug Loading dose	Ixekizumab + CBT / Placebo + CBT Study					
	Week 1	Week 2	Week 3	Week 4			Week 0	Week 2	Week 4	Week 6	Week 8	Week 10
Patient has completed 4 weeks of Unsuccessful Compression Therapy	✓	✓	✓	✓	✓							
Informed Consent					✓							
Medical Hx inc smoking Hx					✓							
Bloods (screening for TB,Hep B & C, HIV)					✓							
Concomitant Medications					✓							
Observations (Weight, BP, Temp)					✓							
Perinuclear Cellulitis (possible exclusion from trial if confirmed)					✓							
Ulcer Assessment + Bx + Swab					✓							
Photos both limbs					✓							
DLQI					✓							
Eligible for the Study												
Ulcer Assessment						✓	✓	✓	✓	✓	✓	✓
Smell / Exudate / Colour							✓	✓	✓	✓	✓	✓
Perinuclear Cellulitis (possible exclusion from study if confirmed)						✓	✓	✓	✓	✓	✓	✓
Photos both limbs						✓	✓	✓	✓	✓	✓	✓
Blood Sample												✓
Skin Bx (All Participants)												✓
Swabs									✓			✓
Collection of Exudate where applicable												
Compression Therapy						✓	✓	✓	✓	✓	✓	✓
Ixekizumab or Placebo S/C Injection						160mg	80mg	80mg	80mg	80mg	80mg	80mg
DLQI												✓
Adverse Events						✓	✓	✓	✓	✓	✓	✓

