## 7.2 Participant Assessments Pre- Registration

- **Assessment of eligibility** – Full skin assessment and has to undergo 4 weeks of compression bandaging for venous ulcer
- Complete medical history including Smoking History
- **Assessment of concomitant medications** will be performed at baseline, during treatment and at all follow-up points throughout the study.
- **Blood Sample** will be taken to screen for (TB, HEP B, C and HIV).
- **Physical examination (weight, temperature, blood pressure)** will be assessed at baseline and at all follow-up points throughout the study
- **Photograph of the Ulcer** will be measured using standard medical photography and will be measured at baseline and follow-up points throughout the study. The size of the ulcer will be monitored from these images.
- **Skin biopsy (all patients)** will be performed on all patients at Baseline and at 12 weeks. Skin Biopsy will not be performed on a participant that has achieved full wound healing.
- **Swab** a swab will be taken of the ulcer at baseline, 6 weeks and at week 12 of the study.
- **Saliva sample (all patients)** will be taken for all patients at Baseline and 12 weeks.
- **Leg circulation** will be assessed by looking for signs of pitting oedema, leg ulcer or intermittent claudication, lower limb pulse palpation. Leg circulation will be assessed by the clinician at baseline and at all follow-up points throughout the study.
- **DLQI** assessment will be completed by patients at baseline and at 12 weeks.

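### Adverse event definitions and reporting start at the first injection, so harms of the research biopsy taken at Pre Screening fall under no stated reporting rule

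*Protocol*

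**What the plan says.** Four places in the protocol fix when safety reporting begins, and they agree.

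- Section 12.1 limits an adverse event to one occurring "in a patient administered a study treatment", and says of the serious category: "An SAE is any untoward medical occurrence that occurs after administration of the Ixekizumab".
- Section 12.2.1: "Adverse events are to be reported following any injection of Ixekizumab".
- Section 12.2.2 runs serious event reporting "from the commencement of injection until the last visit".
- In Table 7.1 the Adverse Events row carries seven ticks, matching the seven injection entries (160 mg, then six of 80 mg). It has none at Pre Screening.

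The biopsy comes earlier. The Table 7.1 row "Ulcer Assessment + Bx + Swab" is ticked at Pre Screening, above the row that marks eligibility and ahead of the loading dose. Section 7.2 says the skin biopsy "will be performed on all patients at Baseline and at 12 weeks". It serves research: section 2.3.2 lists "Treatment-related reduction of IL17 levels in wound fluid and biopsies" among the secondary endpoints. Section 4.3 requires written consent before any screening procedure, so the person biopsied is already a consented participant.

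Under the heading for related unexpected serious events, section 12.1 explains relatedness as "that is, it resulted from administration of any of the research procedures".

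**The concern.** The protocol mandates an invasive procedure on a non-healing leg ulcer, for research purposes, in consented people, and asks for no adverse event record until some later date when an injection is given. Infection or bleeding at the biopsy site in that interval, even if it led to hospital admission, would trigger no adverse event form and no 24-hour report. Nor does any stated rule send it to the safety committee, which section 13.4 says is told at once of serious adverse events.

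People biopsied and then found ineligible are the clearest case. They bear the procedure's risk and never enter the reporting window.

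The relatedness wording shows that the authors had harms of research procedures in mind, not only harms of the drug. The start of reporting does not follow that through. Section 2.2 also places the safety emphasis on infections, one of the harms an ulcer biopsy could cause.

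**Working it through.** No arithmetic applies: no figure in the protocol depends on the reporting window. The check is to put events in time order and ask which rule covers each interval. I read ixekizumab in section 12 as the blinded injection, active or placebo.

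1. **Consent.** Section 4.3 puts it before any screening procedure. Table 7.1 ticks it at Pre Screening.
2. **Biopsy.** Table 7.1 ticks it at Pre Screening, and its other biopsy row is ticked only at the end of treatment. The Pre Screening biopsy is therefore the baseline biopsy that section 7.2 requires.
3. **Eligibility still open.** The screening bloods for tuberculosis, hepatitis B and C and HIV are in the same Pre Screening column, and the eligibility row comes below. Some biopsied people can therefore fail screening.
4. **Randomisation.** Section 4.3 has the criteria checked again before and at this point.
5. **First injection.** The loading dose is a later column of Table 7.1. The definitions in 12.1, both windows in 12.2 and the Adverse Events ticks all start here.

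Coverage of a biopsy harm, by time of onset:

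| Onset | Adverse event or serious event under 12.1? | Inside the 12.2 windows? | Adverse Events tick in 7.1? |
|---|---|---|---|
| Between biopsy and first injection, later dosed | No | No | No |
| After biopsy, never dosed | No | No | No |
| After first injection, up to the last visit | Yes | Yes | Yes |

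The first two rows are the gap. The first applies to all 28 planned participants and ends at dosing. The second applies to every biopsied screen failure and never ends.

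The eligibility rules feed the second row. Exclusion criterion 6 bars ulcer infection in the preceding two months, and the criteria are checked again at randomisation. A participant whose ulcer becomes infected after the biopsy can become ineligible for that reason, is then never injected, and never enters the window. The harm itself can remove the case from reporting.

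**The case against.** The strongest reply is that section 12 is internally consistent. Definitions and windows both start at dosing, which is a recognisable choice for a drug trial. The wording on research procedures concerns relatedness, not timing, and still has a use after dosing, for instance for the week 12 biopsy. It also sits under one definition only: the serious adverse reaction definition, the causality table and the investigator's causality duty in 12.2.2 all refer to treatment.

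This stands, and it rules out a stronger reading that a reader might infer: that a hospitalisation caused by the pre-dose biopsy already qualifies as a related unexpected serious event and is then shut out by the window. It does not qualify. That category requires an adverse event, and 12.1 confines adverse events to people given study treatment. The defect is missing coverage in the definitions and windows together, not a window that contradicts a definition.

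A reader might also infer that a biopsy infection beginning before week 0 would commonly be logged later as a new event and blamed on the blinded treatment. The protocol limits this. Exclusion criterion 6 and the re-check at randomisation should remove such a participant. Table 7.1 has cellulitis, ulcer assessment and photographs at both Pre Screening and the loading dose, and 12.2.2 asks for the date a serious event occurred. What remains is an infection missed at those checks, or one arising between randomisation and first injection. That is a minor residual risk.

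Three smaller points are fair. Figure 1, the reporting flow, is not shown, although nothing in the visible text suggests that it opens the window earlier. Local ethics or regulatory rules might capture some events. The biological endpoints depend on funding, but section 7.2 requires the biopsy without that condition.

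None of this supplies a rule in the protocol for a biopsy harm before dosing.

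**Conclusion.** The point holds as a gap in safety coverage. As written, the protocol does not require reporting of any harm of its own pre-dose biopsy: temporarily for the 28 planned participants, permanently for biopsied screen failures.

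Its size in events cannot be given. The protocol states neither the interval from biopsy to first injection, nor the expected number of screen failures, nor a biopsy complication rate. Neither the primary endpoint nor the week 12 drug-related safety endpoint is affected. The case for change is that people exposed to a mandated procedure should have its harms recorded, and that this is cheap to arrange.

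The conclusion rests on reading Table 7.1 as placing the biopsy at Pre Screening, on a visit before the loading dose. If the baseline biopsy were in practice taken at the loading-dose visit, the interval for dosed participants would nearly vanish, but the table shows no biopsy there. It concerns only the start of the window. Because the protocol itself sets that start, it is not a matter left to the statistical analysis plan.

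**What to change.** - **Section 12.1:** extend the adverse event and serious adverse event definitions to consented participants who have undergone a protocol-mandated procedure, whether or not they are later dosed. Without this, a change to the windows alone would achieve nothing, because a pre-dose event would still not be an adverse event.
- **Sections 12.2.1 and 12.2.2:** report serious adverse events, and adverse events caused by a protocol-mandated procedure, from consent, including in people never dosed. Keep the full adverse event window from the first injection of study treatment.
- **Table 7.1:** tick the Adverse Events row at Pre Screening.
- **Analysis:** list events with onset before the first injection separately from treatment-emergent events, so that the comparison between arms is unchanged.

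The cost is a short amendment to three subsections and one tick in the schedule, plus a few more adverse event forms before dosing, some of them for screen failures. No visit or procedure is added.

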### 3.1 Dosing Regimen

Cohorts of patients with chronic venous ulcers (n = 28) will be randomly assigned to treatment and placebo groups, both receiving compression treatment and standard dressing and therapy of wounds.

Ixekizumab or placebo will be injected subcutaneously (prefilled syringe format) in two 80 mg injection at week 0, followed by single 80mg injections at weeks 2, 4, 6, 8, 10 and 12. This corresponds to standard dosing regimen performed in psoriasis.

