### **4.2 Accrual Numbers and Timelines**

It is anticipated it will take 9 months to complete target accrual of 28 participants. Duration for individual patients on study will be approximately 16 weeks this includes the inclusion criteria of 4 weeks of unsuccessful compression bandaging.

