### 8.1 Protocol Treatment Discontinuation

A participant would be considered to have discontinued treatment where trial related treatment is ceased according to the reason(s) outlined above. The participant may however still agree to further follow-up assessments as scheduled in Section 7.1.

The participants' discontinuation of treatment must be documented in the medical records and transcribed onto the relevant Case Report Form (CRF).

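### SAE reporting stops at the week-12 visit, where the last injection is given, so new events after it have no scheduled capture; two safety sentences also name ixekizumab only

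*Protocol*

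**What the plan says.** **Reporting window.** Protocol 12.2.2 requires sites to report SAEs within 24 hours of being notified, "from the commencement of injection until the last visit". SAEs that have been reported are followed until they resolve.

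**Timing.** Section 3.1 gives two injections at week 0, "followed by single 80mg injections at weeks 2, 4, 6, 8, 10 and 12"; section 6 repeats this. Section 4.2 states: "Duration for individual patients on study will be approximately 16 weeks this includes the inclusion criteria of 4 weeks of unsuccessful compression bandaging". The injection row of the table in 7.1 reads "160mg 80mg 80mg 80mg 80mg 80mg 80mg", with no column after the last injection. Section 7.2 puts a second biopsy at week 12 for participants whose ulcer has not healed. After stopping treatment, a participant may still agree to "further follow-up assessments as scheduled in Section 7.1" (8.1); no separate safety visit is described.

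**Objective.** Section 2.2 names safety alongside efficacy and puts particular weight on infections. The safety endpoint in 2.3.2 is set at 12 weeks.

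**Arms.** Section 12.1 says: "An SAE is any untoward medical occurrence that occurs after administration of the Ixekizumab". Section 12.2.1 says: "Adverse events are to be reported following any injection of Ixekizumab". The AE definition in 12.1, however, refers to study treatment without naming a drug, and the treatment columns in 7.1, including the adverse-event row, are headed for both arms.

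**The concern.** If the last visit is also a dosing visit, the reporting window closes on the day of the last exposure. An infection or injection reaction that begins in the following days, or a wound infection after the week-12 biopsy, would begin outside the SAE window and after the last planned contact. Infection is the safety question this trial singles out, so the gap touches a stated objective. A statistical analysis plan cannot repair it, because it can only analyse what the protocol has collected.

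The drug-specific wording is a second, smaller matter. In a double-blind placebo-controlled trial, the rules for what counts as an SAE and what triggers AE reporting must be the same in both arms. Two sentences are written as if only one arm were dosed.

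**Working it through.** **1. Reproduce the stated duration.** Inputs: compression period 4 weeks (4.2, 6); last injection at week 12 (3.1, 6); time on study about 16 weeks (4.2). Let *f* be the follow-up after the last injection.

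4 + 12 + *f* = 16, so *f* = 0.

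The protocol's figure reproduces only if nothing is scheduled after week 12. The word approximately in 4.2 allows some slack, but 7.1 has no column for a later visit.

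**2. Check that the dosing sections agree.** Section 3.1 gives two 80 mg injections at week 0 (160 mg) and six single ones of 80 mg. The table in 7.1 gives 160 mg and then 80 mg six times. Both give seven dosing visits, so the schedule itself is consistent.

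**3. Scheduled observation after each dose, to the next visit.**

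| Dose at week | Next scheduled visit | Weeks observed |
|---|---|---|
| 0 | 2 | 2 |
| 2 | 4 | 2 |
| 4 | 6 | 2 |
| 6 | 8 | 2 |
| 8 | 10 | 2 |
| 10 | 12 | 2 |
| 12 | none | 0 |

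The zero applies to everyone who receives the week-12 injection. A participant who stops treatment earlier but stays in follow-up is still seen up to week 12.

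**4. What is required for an event that begins after the week-12 visit.**

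- *Site reporting of an SAE (12.2.2):* not required, because the window has closed.
- *Non-serious AE (12.2.1):* no end date is stated, but the CRF takes the highest grade since the previous visit. Collection therefore depends on a next visit, and there is none.
- *Notice to the drug supplier (12.2.1) and to the IDSMC (13.4):* no end date is stated. Both depend on someone learning of the event.
- *SAE already reported:* followed until resolved, so it is not lost.

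The gap is thus confined to events with new onset after the last visit.

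**5. Wording on arms, side by side.**

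| Place | Covers |
|---|---|
| SAE definition, 12.1 | ixekizumab only |
| AE reporting sentence, 12.2.1 | ixekizumab only |
| AE definition, 12.1 | any study treatment |
| AE recording sentence, 12.2.1 | all AEs, no arm named |
| SAE window, 12.2.2 | from first injection, no drug named |
| AE row of the table, 7.1 | both arms |

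Two of the six places are drug-specific. Blinded sites (section 3) could not apply a rule limited to ixekizumab recipients.

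**The case against.** **The last visit is never defined as week 12.** This is true. The reading rests on an approximate duration and on a table whose last column label is missing from the text at hand. Figure 1, on adverse event reporting, and the trial schema are not shown either. Still, 3.1 and 6 fix the seventh injection at week 12 and 7.1 lists nothing after it. A longer window given only in Figure 1 would contradict 12.2.2 and would itself need reconciling.

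**The safety endpoint is set at 12 weeks, and the visits cover it.** This stands for the endpoint as defined, and the primary endpoint is untouched. It limits the severity, but it does not provide observation after the last dose.

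**Stronger readings that the protocol does not support.**

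- A reader might infer that no placebo event would be captured and that the safety comparison has no comparator. The four arm-neutral places listed above and the blinding rule this out.
- A reader might infer that a late SAE could never reach the supplier or the IDSMC. The sentences on notifying them carry no end date. What is missing is scheduled detection and a site duty under 12.2.2.
- The last injection's share of the total dose might be offered as the size of the gap. It measures neither events, person-time nor risk.
- One dosing interval (2 weeks) might be taken as the minimum extension. Nothing in the protocol makes it a safety follow-up period.

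**Conclusion.** The point holds in two parts, and both should be fixed.

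1. The SAE window closes at the visit where the last injection is given, leaving 0 weeks of scheduled observation after that dose, against 2 weeks after each of the six earlier dosing visits. Events with new onset after that visit, including any from the week-12 biopsy, have no planned detection; if serious, they fall outside the site's duty under 12.2.2. That duty also sits awkwardly beside the open-ended sentences on notifying the supplier and the IDSMC, and they should be reconciled. The gap affects every participant who completes dosing, up to 28. How many events would be missed cannot be estimated, because the protocol gives no event rates.

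2. The SAE definition and the AE reporting sentence conflict with the rest of the protocol on which arms they cover. This is a fault of wording.

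The first part assumes that the last visit is week 12 and that neither Figure 1 nor the schema sets a later window.

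**What to change.** Leave dosing as it is.

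- **12.2.1 and 12.2.2:** state that AE and SAE reporting continues for a fixed interval after the last injection, its length set by the sponsor with the drug supplier. Align the sentences on notifying the supplier (12.2.1) and the IDSMC (13.4) with the same end point.
- **4.2 and 7.1:** add one telephone contact per participant at the end of that interval, and restate the time on study. For illustration only, with assumed intervals of 2, 4, 8 or 12 weeks, the 16 weeks would become 18, 20, 24 or 28 (16 plus the interval).
- **12.1 and 12.2.1:** in the SAE definition and the AE reporting sentence, replace ixekizumab with study treatment (ixekizumab or placebo).

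The cost is a wording amendment, one extra contact for each of 28 participants, and a longer time on study by the chosen interval. The week-12 efficacy assessments do not change.
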